#### Randomization and Study Subject Packet Creation

Fully enrolled subjects will be randomized based on a two block randomization generated by the website [www.graphpad.com](http://www.graphpad.com). Randomization will be created so there are two groups (two block randomization), one which will receive 15 mg of intramuscular ketorolac and one which will receive 60 mg of intramuscular ketorolac. Each group (block) will consist of 61 subjects per the power analysis described later in this document and will be assigned a Subject Study Number.

The Subject Study Number will be comprised of a "K" for ketorolac, "15" or "60" designating which dose of ketorolac will be administered and then a specific number reflecting their position within the randomization block (randomization block number). For instance, a Subject Study Number of "K15-30" would signify that this patient was randomized into the ketorolac 15 mg group and the number 30 would reflect both the block to which the patient was randomized and confirm that the patient is indeed in the 15 mg group. Using both "15" or "60" and the randomization block number acts as a checks and balance to ensure that the patient is randomized into the correct group, and that the subject receives the correct randomized dose. Based on the randomization block number it is possible to know into which group the subject was randomized, the dose of ketorolac which will be administered and the order of the patient in the overall randomization. Following randomization, Subject Study Packets will be prepared.

Subject Study Packets will be prepared prior to the data collection (prior to the screening process). These packets will be created using manila envelopes capable of containing all study documents and which can be sealed. The contents of the envelopes will include the (1.) Ketorolac Research Form, (2.) Informed Consent Form (which includes consent for a POC UHCG), (3.) HIPAA Authorization Form, (4.) pretreatment VAS form, and two post-treatment VAS forms. None of the documents utilized or created throughout the study will be entered in to the subjects EHR. The manila packet and all documents contained within it will be annotated with the Subject Study Number (as described above). A description of these forms is listed below.

1. Ketorolac Research Form: this form documents age, gender, pain location, inclusion criteria, exclusion criteria, objective adverse effects, and subjective adverse effects. No PHI or PII will be annotated on this form.
  1. Age will be documented in years only. The actual date of birth will not be documented.
  2. Gender will be documented as "M" for male or "F" for female. Or an appropriate box will be "checked" by the potential subject indicating subject gender.
  3. Pain location will be free text, but will be qualified and isolated to an anatomical region. This will be at the discretion of the investigator. For instance, "heel pain" would be annotated as foot pain, or "calf pain" as leg pain. The anatomical regions designated for the purposes of this research are: (1.) neck pain, (2.) shoulder pain, (3.) arm pain, (4.) elbow pain, (5.) forearm pain, (6.) wrist pain, (7.) hand pain, (8.) hip pain, (9.) thigh pain, (10.) knee pain, (11.) leg pain, (12.) ankle pain, (13.) foot pain or (14.) back pain.
  4. See inclusion and exclusion section in this document for a detailed description of both.
  5. Adverse events which occur due to administration of intramuscular ketorolac will be documented as objective and subjective adverse effects. [Note, "adverse events" is a phrase used to describe adverse events, reactions, and effects to intramuscular ketorolac.] Subjects will be provided a list of known adverse events occurring in greater than 1% of patients during the U.S. Food and Drug Administration (FDA) trials, according to the medical website UpToDate.com. The list of adverse events will be included on the Ketorolac Research Form. Subjects will be advised to circle any of the adverse events that they are experiencing. Each circled adverse event will count as 1 in a binary numbering system (1 indicating an adverse event and 0 indicating no adverse event) for purposes of analysis. Subjects may have more than one adverse event and each event will count as 1 point. The definitions of objective and subjective adverse event are provided below.
    1. Objective adverse events are those identified during reassessment immediately following the initial ketorolac administration, and at the 30 minute and 60 minute re-evaluation intervals. To better facilitate analysis, a list of the most commonly occurring objective adverse events, according to UpToDate.com, will be provided for the investigator to choose from. This list will be included on the Ketorolac Research Form. Objective adverse events are any (1.) subjective events (signs or symptoms) which can be validated or observed by study investigators (such as diaphoresis), (2.) are obvious to the investigator, but perhaps not the patient (mild facial swelling or rash) or (3.) abnormal vital signs. Blood pressure and heart rate measurements will be taken at the 30 minute and 60 minute intervals. Any deviation of blood pressure or heart rate which would meet exclusion criteria for this study would prompt immediate notification of the attending provider and the patient would be excluded from the study.
    2. Subjective adverse events are any symptoms conveyed by the subject, but are not measureable, observable or verifiable by the investigator. To better facilitate analysis, a list of the most commonly occurring subjective adverse events, according to UpToDate.com, will be provided to the study subject to choose from. Examples of subjective adverse events may include dizziness, light headedness or nausea (this is not an exhaustive list of subjective adverse events).
2. Informed Consent Form: this document describes important details and purpose of the research, risks, benefits, alternatives, use of PHI and PII, obtains consent from female potential subjects for a POC UHCG and obtains official consent in the form of the subject's signature. This form will be explained in detail with the patient to ensure their complete and total understanding. The patient will be given as much time as possible to contemplate the decision to enroll as a subject in this study. However, once roomed in the ED, the patient will no longer be eligible to enroll. The patient will be given the opportunity to ask as many questions as possible prior to obtaining signature and will be informed that they have the right to withdraw from the study at any point.
3. HIPAA Authorization Form: signature of this document authorizes investigators use of the subject's protected health information (PHI) and personally identifiable information (PII) responsibly, securely and only for the purposes of this study. PHI and PII will be explained in detail to the patient and all questions will be honored. Should the patient decline to sign this document, they will be excluded from the study.
  1. PHI: The only protected health information used for this study will be the (1.) chief complaint and (2.) vital signs. A review of systems (ROS) will be used for inclusion and exclusion purposes of this study, but the EHR will not be accessed for this information and this information will not be documented on any media. A detailed description of the ROS is provided later in this application.
  2. PII: The only PII used for this study will be the (1.) subject name, (2.) age (in years-not date of birth), (3.) medical record number (MRN) and (4.) gender.

4. VAS forms (pretreatment and post-treatment): these are single page forms with a 0-100 mm VAS. Four separate VAS forms will be included in the Subject Study Packet and will be used to assess the subject's pain prior to administration of ketorolac, and at the 30 and 60 minute intervals after ketorolac administration. A fourth form will be included in the event that the patient completes the VAS incorrectly. The subject in each instance and on separate forms, will be asked to mark a horizontal line on the 0-100 mm continuum indicating their pre-treatment level of pain and their pain level post-treatment at the 30 minute and 60 minute intervals. Three separate forms are utilized to control for response bias. The Subject Study Number will also be included on the document, but otherwise no other information will be contained on the VAS forms.

With the exception of the actual data collection phase of this study, the Subject Study Packets will be secured in a locker within the WBAMC ED which can only be accessed by the investigators. The locker will be padlocked and access to the room containing the locker requires key-card access and cypher lock access (a code entered into the automated door lock prior to being able to open it). The Subject Study Packets will remain in this location throughout the data collection phase, but will then be transferred securely to WBAMC room 10015 (the emergency medicine physician assistant resident room) for at least three years following completion of the study (for auditing purposes). Upon completion of the three year, post-study period, the documents will be destroyed in accordance with WBAMC local policy and procedure for destruction of such documents.

A hard-copy master key will be created to bridge the study subjects' de-identified Ketorolac Research Forms with the excel document which will be used to compile all of the study data. The master key will annotate the (1.) Subject Study Number., (2.) name and (3.) MRN. The information which the master key holds will be collected only after the patient has been consented and enrolled in to the study but prior to administration of the medication. This document will be maintained for the sole purpose of identifying subjects for the duration of data collection and analysis period. This document will be a hard copy document on standard sized printer paper within a document sized manila envelope. It will be secured by the investigator in the same manner as the other documents.

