##### Definitions

1. Acute – onset of symptoms within 30 days on the day of data collection.
2. Musculoskeletal (MSK) – a general term used to described the various forms of pain effecting the musculoskeletal system, for this study. The types of pain included in this definition are undifferentiated muscular, undifferentiated bony, undifferentiated soft tissue, neck, back (to include cervical, thoracic, lumbar, and sacral), shoulder, arm, elbow, forearm, wrist, hand, hip, thigh, knee, leg, ankle, foot and digits).
3. Potential subject – any patient presenting to the WBAMC ED meeting age inclusion criteria with an Emergency Severity Index (ESI) score of 4 or 5 and having a chief complaint of musculoskeletal (MSK) pain, as defined above.
4. Subject – any potential subject meeting aforementioned criteria for enrollment, who met all inclusion criteria, who did not meet any exclusion criteria, who provided informed consent, and signed the Healthcare Information Portability and Accountability Act (HIPAA) Authorization Form.
5. Subject Study Packet –the packet containing documents used to annotate eligibility, acceptance, and consent to participate in the study. Forms included within the packet are the Ketorolac Research Form, Informed Consent Form, HIPAA Authorization Form, and VAS forms (1-3).

Subject Study Number – The randomized number assigned to each subject in order to de-identify data for purpose of protecting Personal Identifiable Information during the reporting of the study's results.

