Potential subjects who grant verbal willingness to participate in this study will then be formally consented. The consent process includes a complete description of the study to include objectives of the study, benefits to the DoD, process, subject time commitment, risks, benefits, alternatives and documentation to be completed by subject. Only after the consent process is described, all of the inclusion criteria are met and none of the exclusion criteria are met, will potential subjects be fully screened. This includes females being screened for pregnancy using a point-of-care (POC) urine human chorionic gonadotropin (UHCG) test (urine pregnancy test). Additionally, to complete enrollment in to the study, subjects will be asked to sign the HIPAA Authorization Form. The HIPAA Authorization Form authorizes investigators access to protected health information (PHI) and Personally Identifiable Information (PII) for purposes only pertaining to this study.

Named investigators on this protocol will conduct the consent process for all subjects enrolled in this study.

Potential subjects who grant verbal willingness and permission to participate in this study will then be consented. The consent process includes a complete description of the study to include objectives of the study, benefits to the DoD, process, subject time commitment, risks, benefits, alternatives and documentation. Only after the formal consent process is described, all of the inclusion criteria are met and none of the exclusion criteria are met, will potential subjects be officially consented using the Informed Consent Form attached with this protocol submission.

Female potential subjects will be consented for a point-of-care (POC) urine human chorionic gonadotropin (UHCG) test (urine pregnancy test).

Upon meeting all of the aforementioned criteria for enrollment, providing a signature on the Informed Consent Form and HIPAA Authorization Form, the potential subject will be considered enrolled as a subject for the study.

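### The subject number states the dose and appears on the packet and every form, so allocation is not concealed from recruiters and the single-blind label is unsupported

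*Protocol*

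**What the plan says.** Protocol section 10.1, Randomization and Study Subject Packet Creation, sets out the following.

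- **Content of the number.** It is K, then 15 or 60 for the dose, then a position number. Of the position number the protocol says that "it is possible to know into which group the subject was randomized, the dose of ketorolac which will be administered".
- **Timing.** "Subject Study Packets will be prepared prior to the data collection (prior to the screening process".
- **Container.** "These packets will be created using manila envelopes capable of containing all study documents and which can be sealed".
- **Where the number goes.** "The manila packet and all documents contained within it will be annotated with the Subject Study Number (as described above". The description of the VAS forms repeats that each one bears it.
- **When subjects are randomized.** "Fully enrolled subjects will be randomized based on a two block randomization generated by the website".
- **Access.** Outside actual data collection, "the Subject Study Packets will be secured in a locker within the WBAMC ED which can only be accessed by the investigators".

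The Definitions in 10.1 list the contents: "Forms included within the packet are the Ketorolac Research Form, Informed Consent Form, HIPAA Authorization Form, and VAS forms (1-3". Section 13.4 states: "Named investigators on this protocol will conduct the consent process for all subjects enrolled in this study".

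Under Medication Administration, the principal investigator tells the attending provider the randomized arm. The attending signs the Ketorolac Research Form to agree to that dose, or may reject it, and the patient is then excluded. The dose given follows the number on the randomized packet that was assigned to the subject.

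Sections 9.4 and 9.6 describe the trial as single-blind. Neither says who is blinded. The SAP mentions neither blinding nor masked arm codes.

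**The concern.** Two protections are involved, and the numbering scheme affects both.

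**Concealment** keeps the next arm unknown until the patient is irrevocably in the trial. Entry here leaves room for judgement: the review of systems is not documented (10.1), and a patient may be excluded for any other medical concern (14.2). A recruiter who can read the arm from the packet can, even without intent, approach, persuade or screen differently by arm. The attending's right to reject a known dose, followed by exclusion, opens a second such route after randomization.

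**Blinding** matters because the primary outcome is self-reported pain and the secondary outcome is adverse events that subjects circle or investigators judge.

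In a non-inferiority trial a shift in either direction does harm. A shift against 15 mg costs power. A shift in favour of 15 mg raises the chance of declaring non-inferiority falsely.

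**Working it through.** **Step 1. Who can know the arm, and when**

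| Party | Role | How the arm reaches them |
|---|---|---|
| Investigators | Hold packets, recruit, consent, assess, measure the VAS, categorise adverse events (10.1, 10.2, 13.4) | Coded packet, available before consent |
| Attending provider | Accepts or rejects the randomized dose (10.1) | Told the arm; signs the numbered form |
| Nurse | Prepares and gives the injection (10.1) | The order itself |
| Subject | Marks three VAS forms, circles adverse events (10.1) | Number on each form |
| Statistician | Analyses the worksheet (10.2) | Number is the only identifier kept |

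The consent and HIPAA forms and the form that records eligibility are all in the packet. A coded packet is therefore in use before enrolment is complete.

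**Step 2. Does any safeguard hide the code?**

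- Sealing the envelope does not hide a number written on the packet.
- The locker admits the same people who recruit.
- Randomizing only fully enrolled subjects does not fit packets made up before screening and numbered by arm. The two statements need to be reconciled.
- No section requires packets to be taken in order, or the arm to stay hidden until enrolment is complete.
- Deleting the 15 or 60 alone would not be enough, because by the protocol's own account the position number also gives the group.

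**Step 3. What is left of single-blind?** The investigator, attending and nurse know the dose. The likeliest blinded party is the subject, who handles forms showing 15 or 60 in plain figures.

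**Step 4. Illustration of what a shift would do.** The inputs from section 11.5 are margin 13 mm, SD 27 mm, true difference 0, one-sided alpha 0.05, and 55 evaluable (61 enrolled) per arm. The shift *b* of 2 or 5 mm is my assumption; the documents give none.

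Standard error = 27 × √(2/n), which is 5.149 at n = 55 and 4.889 at n = 61. Power comes from the noncentral t with 2n − 2 degrees of freedom.

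The plan's figure reproduces: at n = 55 the noncentrality is 13/5.149 = 2.525 and power is 0.806. At n = 54 it is 0.7998, so 55 is the smallest n that reaches 80%.

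- Shift against 15 mg, true difference 0: noncentrality (13 − b)/SE.
- Shift in favour of 15 mg, true difference at the margin: noncentrality b/SE.

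| | b = 0 | b = 2 mm | b = 5 mm |
|---|---|---|---|
| Power, 55 per arm | 0.806 | 0.684 | 0.460 |
| False non-inferiority, 55 per arm | 0.050 | 0.104 | 0.248 |
| Power, 61 per arm | 0.841 | 0.723 | 0.493 |
| False non-inferiority, 61 per arm | 0.050 | 0.108 | 0.265 |

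**The case against.** **The text hints at an orderly sequence.** The master key is filled in only after consent and enrolment (10.1, although 14.5 places this in recruitment). Medication Administration speaks of enrolling and then randomizing. Section 13.1 turns away late joiners who would disturb the randomization. These suggest good intent, but none of them hides the code from the recruiter.

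**The text does not date the numbering.** The protocol dates the preparation of the packets, not the writing of the number on them. This stands: numbering before screening is an inference. It is a strong one, because the number is described as belonging to a randomized packet that is later assigned to a subject.

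**Measurement bias is limited.** Section 10.2 defers all VAS measurement to the end of the study and requires the investigators to agree on each reading. That leaves little room for biased measurement of the marks. It does not touch selection at entry, what the subject reports, or the categorising of adverse events.

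**Stronger readings the documents do not support.**

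- A reader might infer that subjects are unblinded in fact. No section says that they are told what the number means, and the consent text was not available.
- A reader might infer that the statistician was meant to be blinded. Nothing says so.
- A reader might infer that the protocol makes a false claim of concealed allocation. It makes no such claim; only the single-blind label is at issue.
- A reader might infer that the packet description in 14.5, which omits the consent form, is a contradiction. Removing signed forms for separate storage would explain it.

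**Conclusion.** The point holds and should be fixed before enrolment. As written, the plan lets recruiters know the arm before consent and eligibility are final, lets a patient be excluded after the arm is known, and does not support its single-blind label.

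The conclusion on concealment rests on the plain content of the number, who holds the packets, and the absence of any rule on order or opening. It assumes that numbers are written when the packets are prepared. The conclusion on blinding assumes that the subject is the intended blinded party; whether subjects would decode the number remains unknown.

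The size of any bias cannot be derived from the documents. A reader might infer from the illustrative figures that the trial is biased toward non-inferiority. They show only how sensitive the test is to a small assumed shift in either direction, and they are not evidence that a shift exists.

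**What to change.** 1. Use dose-neutral sequential numbers, 001 to 122, with no dose or block meaning, on packets and all forms. Take them strictly in order.
2. Put each allocation on a card in a sealed opaque envelope bearing the same number. Open it only after consent, eligibility and the pre-treatment VAS mark are complete. Only the mark is needed at that moment, not its measurement. At present the mark is made while the drug is being prepared, so the order of steps must be reworded.
3. Before opening, record on the eligibility form whether the attending accepts either study dose for that patient, so that a refusal falls before the arm is known. Record any later change on the card, keep the patient in the randomized count, and report such changes by arm. The attending's clinical authority is unchanged.
4. Have the list and envelopes prepared and held by someone already available who does not recruit, assess, measure the VAS, categorise adverse events or analyse the data. Keep the key and opened cards apart from the forms and the worksheet until VAS measurement and adverse-event categorisation are done.
5. State in 9.4 who is blinded. If it is the subject, acknowledge that injection volume may give the dose away. From the vial strengths in 9.2, 15 mg is 0.5 mL (15/30) or 1 mL (15/15), and 60 mg is 2 mL (60/30) or 4 mL (60/15). The vials to be used are not stated.
6. The SAP refers to a decision already made during analysis. If enrolment is complete, items 1 to 4 come too late: drop or qualify the single-blind label and report the unconcealed allocation as a limitation.

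The cost is 122 envelopes and cards, some time from a list holder, rewording of the randomization and medication parts of 10.1 and of 9.4, and a small change in workflow. No extra visits are needed.

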There is a very low risk for harm with participation in this study as the medication is being administered as recommended by the package insert and as recommended by the Food and Drug Administration. Furthermore, patients who are at increased risk for these adverse events will not be enrolled in the study, based on questions asked using the inclusion and exclusion criteria during the consent process. Ketorolac has the following known adverse events with applicable percent of patients who experience these effects: headache (17%), gastrointestinal pain (13%), dyspepsia (12%), nausea (12%), edema (4%), hypertension, dizziness (7%), drowsiness (6%), diaphoresis, pruritus, skin rash, diarrhea (7%), constipation, flatulence, gastrointestinal fullness, gastrointestinal hemorrhage, gastrointestinal perforation, gastrointestinal ulcer, heartburn, stomatitis, vomiting, anemia, prolonged bleeding time, purpura, increased liver enzymes, pain at injection site (2%), tinnitus, and renal function abnormality.

Additionally, there is a risk that the study subjects receiving the 15 mg dose will have inadequate pain control.

There is also the risk of accidental disclosure of protected health information (PHI) or personally identifiable information (PII). However, name and MRN will only be listed on the Master Key. The remainder of the research data will only have the Study Subject Number.

There are specific risks to pregnant and breastfeeding women. There is an FDA boxed warning that ketorolac is contraindicated in labor and delivery due to the potential to inhibit uterine contractions and adverse effects on fetal circulation. Additionally, ketorolac has a pregnancy risk factor of C. In this category, risk to the mother and fetus cannot be ruled out.

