#### **14.3**

#### **Confidentiality Protections (for research records, data and/or specimens):**

Describe in detail the plan to maintain confidentiality of the research data, specimens, and records throughout the study and at its conclusion (e.g., destruction, long term storage, or banking). Explain the plan for securing the data (e.g., use of passwords, encryption, secure servers, firewalls, and other appropriate methods). If data will be shared electronically with other team members/collaborators outside the institution, describe the method of transmission and safeguards to maintain confidentiality. Explain whether this study may collect information that State or Federal law requires to be reported to other officials or ethically requires action, e.g., child or spouse abuse

Study subjects will not be identified by their name, social security number, or medical records number (MRN) for the production of the final manuscript, poster, or any publication of the findings of this research. The master key used to identify study subjects will be maintained by the investigator for the duration of the study then destroyed once all data has been transferred from the Ketorolac Research Forms to the excel worksheet. All reportable data will be de-identified and collected on the Ketorolac Research Form and the VAS forms. The documents will be held in a locked locker in the WBAMC ED for the duration of the data collection period, analysis period, and as the manuscript is produced. Upon completion of the manuscript, the documents will be securely transferred to the WBAMC room 10015 and secured in a locked cabinet for a period of up two years. Upon completion of the two-year post-study period, the documents will be destroyed in accordance with WBAMC sensitive document disposal policies.

All data used for analysis will be compiled using Microsoft Excel into a table for ease of reporting. This, password protected, electronic document will be created and stored on a U.S. government issued laptop authorized to create and hold PHI and PII. This laptop is individually issued to the PI, CPT [name], and he is the only person who will have access.

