#### **14.5 Privacy for Subjects:**

Describe the measures to protect subject's privacy during recruitment, the consent process, and all research activities, etc.

During the recruitment phase, the subjects' name, MRN, and Subject Study Number will be annotated on the master key. The master key will be a paper document which will be maintained by the investigator for the duration of the study. It will be secured in a padlocked locker within the WBAMC ED for the duration of the study.

The recruitment phase will be initiated in the waiting room by requesting them to step off to a more private, secluded portion, where they will be given the verbal synopsis (enclosed) by the PI or AI. Within this secluded portion, an enclosed room, within the Emergency Department the potential subject will complete the pre-screening and consent processes.

During the consent process, the study subjects will fill-out, sign, and date Informed Consent Form and HIPAA Authorization Form. These forms, with PII, will be maintained and secured in the same manner as the master key. The Subject Study Packets, containing the Ketorolac Research Form and VAS forms, will contain PHI but no PII as these forms will be annotated with only the Subject Study Number and will be de-identified (no PII will be on these documents). However, these forms will be secured in the same manner as the other forms.

Upon completion of the data collection phase, all forms will be transferred securely to WBAMC room 10015 and secured in a locked cabinet or locker, behind a locked door (secured with a cypher lock) for a minimum of two years following the completion of this study, in accordance with IRB and WBAMC policies.

The single electronic document will be the Excel worksheet used to compile all study subject data. The document will be located on the PIs government issued laptop. This worksheet will be password protected and saved to the hard drive of the PIs laptop. The hard drive on the computer can only be accessed by the person who saved it and network system administrators. All measures have been created to protect the information of the study though there will not be any PHI or PII on the document. This document will be destroyed upon completion of the dissertation defense.

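### Consent, HIPAA and eligibility forms sit in packets already numbered by arm, so allocation is readable before enrolment, opened packets have no rule, and a second name-to-number link remains

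*Protocol*

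**What the plan says.** Protocol 10.1, Definitions, item 5, describes the Subject Study Packet as "the packet containing documents used to annotate eligibility, acceptance, and consent to participate in the study", and lists the Ketorolac Research Form, consent form, HIPAA authorization and VAS forms as its contents. The Randomization and Study Subject Packet Creation part of 10.1 repeats that list, has the packets made up before screening begins, and says: "The manila packet and all documents contained within it will be annotated with the Subject Study Number". The number is a K, then 15 or 60 for the dose, then the place in the list (K15-30 is the protocol's example). Item 1 of the form descriptions puts the inclusion and exclusion criteria on the Research Form.

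The same part opens with: "Fully enrolled subjects will be randomized based on a two block randomization". At the end of the Prescreening / Recruitment part, a person counts as enrolled once all criteria are met and the consent and HIPAA forms are signed.

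On identity, section 14.1 says that "name and MRN will only be listed on the Master Key". Section 14.5 says the signed consent and HIPAA forms hold PII. It then describes the packets as the Research Form and VAS forms, which "will contain PHI but no PII as these forms will be annotated with only the Subject Study Number". Under section 14.3 the master key is to be "destroyed once all data has been transferred from the Ketorolac Research Forms to the excel worksheet".

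**The concern.** Three things follow if the packet text is carried out as written.

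- **Concealment.** The person taking consent and judging eligibility has the arm in view while doing so. In a trial of two doses of one drug, a belief about which dose suits which patient could then influence who is enrolled. Randomisation protects the comparison only if that decision is made without knowing the allocation.
- **Unused numbers.** A packet opened for someone who does not sign, or who signs and then fails a check, carries one of 61 numbers in its arm. The plan does not say whether that number is spent, reissued or replaced.
- **Identity.** Signed pages bearing a name would carry the same number as the VAS and adverse-event data, although the IRB is told that only the master key makes that link.

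**Working it through.** **1. Order of events, from 10.1**

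(a) Packets are numbered by arm and list position before screening. (b) The envelope and every form in it show that number. (c) Eligibility is entered on the packet's Research Form, and the packet's consent and HIPAA forms are signed. (d) The person is then enrolled. (e) Only enrolled subjects are randomised.

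Step (c) uses a form from a particular numbered packet, so the arm is already fixed and visible there. Step (e) cannot then follow step (d). Because the envelope is marked too, sealing it does not hide the arm.

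There is room for discretion at step (c). Section 14.2, item 4, excludes people with any other medical concern found in the history or review of systems, and 10.1 (Medication Administration) says the review of systems is not written down. A choice influenced by the visible arm would leave little trace.

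Attending concurrence is a separate case. 10.1 makes agreement with the randomised dose part of the eligibility record, and that can only follow allocation.

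**2. Sample size**

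Inputs from section 11.5: margin 13 mm, true difference 0, SD 27, one-sided alpha 0.05, equal-variance t-test.

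Power = P(T > t(0.95, 2n − 2)), with T noncentral t and noncentrality 13 / (27 × √(2/n)).

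The plan's own figure: at n = 55, noncentrality = 13 / (27 × 0.1907) = 2.52 and power is 80.6%, so the stated 80% reproduces. At n = 54 power is 79.98%, so 55 is the smallest size that reaches 80%. The allowance is 55 × 0.10 = 5.5, rounded to 6, giving 61.

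Those six numbers are already committed to dropout or withdrawal: 61 × 0.90 = 54.9. Nothing is spare for numbers lost before enrolment. The documents give no rate for that loss, so the rates below are assumptions. Evaluable n is rounded down.

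| Numbers lost before enrolment | Evaluable per arm after 10% loss | Power |
|---|---|---|
| 0% (or all reissued) | 61 × 0.90 = 54.9, taken as 54 | 80.0% |
| 5% | 61 × 0.95 × 0.90 = 52.2, taken as 52 | 78.6% |
| 10% | 61 × 0.90 × 0.90 = 49.4, taken as 49 | 76.5% |

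**3. Identity**

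By 10.1 the consent and HIPAA forms carry the study number; by 14.5 they carry PII. Name and number are therefore together on paper outside the master key, contrary to 14.1. The 14.5 account of packet contents also conflicts with both lists in 10.1. The key is destroyed after transcription (14.3), while the paper stays for at least three years (10.1), up to two (14.3), a minimum of two (14.5), or both two and three (10.14). During that time the signed forms still link name to number.

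**The case against.** The strongest reply is that the protocol speaks of subjects, not packets. 10.1 and section 11.4 give 61 subjects per arm, and Definitions, item 4, makes a subject someone eligible and consented. A reader might infer from the packet text that each arm is really 61 packets, that non-enrollers certainly consume them, and that the trial is underpowered. The documents do not support that. Nothing forbids reissuing an unused number. People who decline at the verbal synopsis (13.1, 13.4) need no packet. Age, triage score, complaint and vital signs are prescreened from the home screen. One paragraph of 13.4 puts signature after the criteria are met. This stands: slot loss is possible, not established.

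Reissue is not a clean answer, however. Consent for the pregnancy test is on the packet's consent form, and another paragraph of 13.4 places that test within screening at the consent stage, so a person can sign a numbered form and then fail. Reissue would put one number on two signed forms, and whoever decided on it could read the arm.

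A reader might also infer that the confidentiality safeguard does not exist. That goes too far. 14.5 secures the signed forms as it does the master key, 10.1 specifies a padlocked locker behind key-card and code access, and the worksheet is de-identified. A link during the study is planned in any case. What remains is a conflict between passages and a second link that the IRB was told is absent.

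**Conclusion.** The concern holds in three parts of different strength. The contradiction over when randomisation happens, and the visibility of the arm before consent and eligibility are settled, follow directly from the text and matter most. They expose the trial to selection bias; they do not show that any would occur, and its size cannot be calculated from the documents. The identity conflict also needs no assumption, but it is a matter of consistency and of what the IRB was told, not a failure of all protection. The power effect is conditional and modest: about 1.4 to 3.5 percentage points below 80%, assuming that 5% to 10% of numbers are lost before enrolment, that none is reissued and that the full 10% loss also occurs. It is zero if numbers are reissued.

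**What to change.** Reconcile 10.1 (Definitions, item 5, and packet creation) with 14.1, 14.3 and 14.5, as follows.

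- Keep the consent form, HIPAA authorization and pre-allocation eligibility page as an unnumbered set, stored apart from the data packets.
- After consent, pregnancy test and eligibility checks are complete, take the next packet in sequence. It should be opaque and sealed, with the arm not readable from the outside, and hold only the numbered data form and VAS forms.
- Record attending concurrence with the randomised dose after allocation, on the numbered form.
- State that an assigned number is not reissued, and that anyone lost after assignment, including through dose rejection, is counted and reported in the assigned arm. Section 13.6 already keeps a separate record of withdrawals and exclusions without identifiers, which could hold the count, arm and reason.
- Set one retention period for the master key and paper forms, replacing the differing statements in 10.1, 10.14, 14.3 and 14.5.

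The cost is protocol wording and repacking, with no extra patients or data. The small downside is two sets of forms per subject, with the master key needed to match consent to data at audit. The retention period chosen for the key has to allow for that.
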